# 7.3.2 Safety Assessments

Adverse events (AEs) will be monitored at each scheduled visit and throughout the study. Toxicity will be assessed using the most recent National Cancer Institute (NCI) guidance: the most recent version of the Common Terminology Criteria for Adverse Events (CTCAE) version 5.0.

# 7.3.3 Study Treatment

Treatment information is detailed in Agent Administration (Section 7.6).

# 7.4 Duration of Therapy and Criteria for Removal from Study

Patients will be removed from study when any of the criteria listed apply. The reason for study removal and the date the patient was removed must be documented in the Case Report Form.

In the absence of treatment delays due to adverse event(s), treatment may continue until one of the following criteria applies:

- Disease progression by RECIST criteria v1.1 (Appendix E) or bone progression per PCWG3 (see Section 7.4.1)
- Disease progression by symptomatic assessment
- PSA doubling from baseline value, confirmed by a second value at least 4 weeks apart, with a minimum time since initiation of therapy of 12 weeks (see **Section 7.4.1**)
- Intercurrent illness that prevents further administration of treatment
- Unacceptable adverse event(s): toxicity (defined in **Section 8.1**) that has not recovered in 2 weeks or if the same toxicity recurs at the decreased dose (unless there is strong evidence of clinical benefit to justify continuation of dosing with study treatment, and the rationale must be discussed with the Principal Investigator before a decision is made)
- The subject or legal representative (such as a parent or legal guardian) withdraws consent for treatment
- If, in the opinion of the Investigator, a change or temporal or permanent discontinuation of therapy would be in the best interest of the subject
- Patient is noncompliant with respect to taking drugs, keeping appointments, or having tests required
- for the evaluation of drug safety and efficacy Bone marrow findings consistent with myelodysplastic syndrome (MDS)/acute myeloid leukemia (AML)
- Potential Hy's Law cases (AST or ALT ≥3x ULN and TBL ≥2x ULN with no other reason)

Because an excessive rate of withdrawals can render the study uninterpretable, unnecessary withdrawal of patients should be avoided. When a patient discontinues

treatment early, the investigator should make every effort to contact the patient and to perform a final evaluation. The reasons for withdrawal should be recorded.

# 7.4.1 Disease Progression

Progression will be evaluated on the basis of biochemical, radiographic, or symptomatic progression based on PCWG3 criteria, or by PSA doubling from baseline. Determinations of disease progression will be made by the investigator.

Progression will be defined as follows:

- 1. Radiographic progression defined by at least one of the following:
  - Soft tissue disease progression by modified RECIST criteria v.1.1 (See Appendix E)
  - Development of two or more new bone lesions not consistent with tumor flare per PCWG3. (If unclear, can repeat a bone scan in 6 weeks.)
- 2. Symptomatic or clinical progression defined by one of the following:
  - Development of a skeletal related event (SRE) defined as pathologic fracture, spinal cord or nerve root compression, palliative radiation to bone, or surgery to bone
  - Worsening pain due to CRPC unable to be controlled by non-narcotic or narcotic medications
  - Sustained worsening of ECOG status resulting from CRPC (e.g., 2 to 3)
  - Treating physician decided to initiate new systemic anti-cancer therapy
- 3. PSA doubling from baseline value, confirmed by a second value at least 4 weeks apart, with a minimum time since initiation of therapy of 12 weeks

We will encourage investigators to continue study treatment until radiographically confirmed disease progression or PSA doubling from baseline requires initiation of new systemic antineoplastic therapy.

#### **7.4.2 EOT Visit**

Upon treatment discontinuation, patients will have an EOT Visit within 28 days of the last dose of ascorbic acid or olaparib, whichever is later. This visit will consist of the following:

- Conduct physical exam (including vital signs, weight)
- Perform laboratory tests: complete blood count w/diff, PSA, comprehensive metabolic panel
- Assess performance status (ECOG) (Appendix A)
- Review concurrent medications
- Assess AEs
- If patient is discontinuing participation in study, perform radiographic tests: CT C/A/P and NM bone scan (if these have not been performed in the prior 3 months)
- Blood and urine research samples

# 7.5 Duration of Follow Up

Subjects will be followed for adverse events for a minimum of 30 days after the last dose of study drug or death, whichever occurs first. Subjects removed from study for unacceptable adverse event(s) will be followed until resolution or stabilization of the adverse event, initiation of new therapy for their cancer, or death, whichever occurs first.

Subjects who discontinued study treatment without documented disease progression should continue to be monitored for disease status by radiologic imaging. Disease monitoring should continue to be assessed every two months (+/- 2 weeks) until: 1) start of a new antineoplastic therapy (information of the new cancer therapy will be collected), 2) disease progression, 3) death, 4) withdrawal of consent, or 5) study closure, whichever occurs first.

Details of first and subsequent therapies for cancer and/or details of surgery for the treatment of cancer, after discontinuation of treatment, may be collected. Reasons for starting subsequent anti-cancer therapies including access to other PARP inhibitors or investigational drugs will be collected and included in the exploratory assessments of survival.

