# 9.1.2 Serious Adverse Event (SAE)

The investigator must assess each event to determine if it meets the criteria for classification as an SAE or serious adverse drug reaction.

All SAEs (including death) occurring from the first dose study drug, throughout the study, and 30 days after the last dose of study drug or before initiation of a new antineoplastic treatment (whichever comes first) must be reported. All SAEs that the investigator considers related to the study drug occurring after the follow-up periods must be reported.

A serious adverse event is an AE occurring during any study phase (i.e., screening, run-in, treatment, wash-out, follow-up), at any dose of the study drugs that fulfills one or more of the following criteria:

- Results in death
- Is life threatening (defined as an event in which the subject was at risk of death at the time of the event; it does not refer to an event which hypothetically might have caused death if it were more severe)
- Requires inpatient hospitalization or causes prolongation of existing hospitalization (see note below for exceptions) for >24 hours
- Results in persistent or significant disability or incapacity
- Is a congenital anomaly/birth defect (note: reports of congenital anomalies/birth defects must also be reported on the Pregnancy Form)
- Is an important medical event (defined as a medical event(s) that may not be immediately life-threatening or result in death or hospitalization but, based upon appropriate medical and scientific judgment, may jeopardize the subject or may require intervention [e.g., medical, surgical] to prevent one of the other serious outcomes listed in the definition above.) Examples of such events include, but are not limited to, intensive treatment in an emergency room or at home for allergic bronchospasm; blood dyscrasias or convulsions that do not result in hospitalization), potential drug induced liver injury, hemophagocytic lymphohistiocytosis
- Suspected transmission of an infectious agent (e.g., pathogenic or nonpathogenic) via the study drug is an SAE.
- Is a new cancer that is not a condition of the study (see clarification below)
- Is associated with an overdose

Events **not** considered to be SAEs are hospitalizations for:

- Admissions as per protocol for a planned medical/surgical procedure or to facilitate a procedure
- Routine health assessment requiring admission for baseline/trending of health status (e.g., routine colonoscopy)

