#### **9.1.8 Deaths**

All deaths that occur during the study, or within the protocol-defined 30-day post-study follow-up period after the administration of the last dose of study treatment, must be reported as follows:

Death clearly the result of disease progression should be reported to the study monitor at the next monitoring visit and should be documented in the eCRF but should not be reported as an SAE.

When death is not due (or not clearly due) to progression of the disease under study, the AE causing the death must be reported to the study monitor as an SAE within **24 hours** (see **Section 9.5.1** for further details). The report should contain a comment regarding the co-involvement of progression of disease, is appropriate, and should assign main and contributory causes of death. This information can be captured in the 'death eCRF'.

Deaths with an unknown cause should always be reported as an SAE. A postmortem may be helpful in the assessment of the cause of death, and if performed a copy of the postmortem results should be forwarded to AstraZeneca and McGuff within the usual timeframes.

The NCI CTCAEv5.0 will be used for adverse event descriptions and grading.

Follow-up of adverse events should continue until the event and any sequel resolve or stabilize at a level acceptable to the investigator and the medical monitor.

Events that are **not** considered serious adverse events include:

- Routine treatment or monitoring of the studied indication, nor associated with any deterioration in condition, or for elective procedures
- Elective or pre-planned treatment for a pre-existing condition that did not worsen emergency outpatient treatment for an event not fulfilling the serious criteria outlined above and not resulting in inpatient admission
- Respite care

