# 9.5 Reporting Adverse Events

# **9.5.1 Reporting Adverse Events (AEs) and Serious Adverse Events (SAEs)** All AEs (both expected and unexpected) occurring from the first dose of study drug

All AEs (both expected and unexpected) occurring from the first dose of study drug will be captured on the appropriate study-specific case report forms (CRFs).

All AEs experienced by subjects will be collected and reported from the first dose of the investigational agent, throughout the study, and will be followed for 30 days after last dose of study drug unless related to the investigational agent.

All SAEs (including death) occurring from the first dose study drug, throughout the study, and 30 days after the last dose of study drug or before initiation of a new antineoplastic treatment (whichever comes first) must be reported. All SAEs that the investigator considers related to the study drug occurring after the follow-up periods must be reported.

In addition, all SAEs, regardless of causality to study drug and/or administration device, will be reported promptly to the IND sponsor (e-mail: [contact], [contact] ), and [contact], within 24 hours of recognition of the event (Appendix B). If this falls on a weekend or holiday, an email notification is acceptable but must be followed by an SAE reporting form on the next business day.

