### 9.5.2 Follow-up of Adverse Events and Serious Adverse Events

After the initial AE or SAE report, the investigator is required to proactively follow each subject and provide further information to the safety department concerning the subject's condition.

All AE(s) and SAE(s) will be followed until:

- Resolution
- The condition stabilizes
- The event is otherwise explained

- The subject is lost to follow-up
- Death

As soon as relevant information is available, a follow-up SAE report will be submitted to the Protocol Chair, Monitors, AstraZeneca, and McGuff.

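### The safety follow-up clauses disagree on whether new cancer therapy is a stopping point, and one reading leaves the four-week status needed by the Section 13.6 stopping rule unobserved

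*Combined protocol and SAP*

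**What the plan says.** Two kinds of rule are involved: how long new events are collected, and how long a known event is followed.

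**Collecting new events.** Section 7.5 sets a floor for everyone: "Subjects will be followed for adverse events for a minimum of 30 days after the last dose of study drug or death". Section 9.5.1 says adverse events "will be followed for 30 days after last dose of study drug unless related to the investigational agent". Serious events, including deaths, have a different end in Sections 9.1.2 and 9.5.1: those up to "30 days after the last dose of study drug or before initiation of a new antineoplastic treatment (whichever comes first) must be reported". There is an exception: "All SAEs that the investigator considers related to the study drug occurring after the follow-up periods must be reported". Section 9.1.8 requires every death within 30 days of the last dose to be reported and does not mention new therapy.

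**Following a known event.** For subjects removed for unacceptable toxicity, Section 7.5 says they "will be followed until resolution or stabilization of the adverse event, initiation of new therapy for their cancer, or death, whichever occurs first". Section 9.1.8 says: "Follow-up of adverse events should continue until the event and any sequel resolve or stabilize at a level acceptable to the investigator". Section 9.5.2 opens with "All AE(s) and SAE(s) will be followed until" and lists resolution, stabilization, another explanation, loss to follow-up and death.

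**Scheduled contacts.** Section 7.4.2 says "patients will have an EOT Visit within 28 days of the last dose of ascorbic acid or olaparib, whichever is later". The Section 7.1 calendar marks adverse-event notation at that visit and in the long-term follow-up column. Section 7.5.1 describes long-term follow-up as a six-monthly phone or chart contact and does not list adverse events among its data.

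**The concern.** Safety and tolerability is the first secondary objective, and Section 4.2.8 says there are no clinical data on this combination in this disease. If sites apply different end points, the same event may be recorded, reported or followed at one site and not at another.

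The sharper problem is the stopping rule. Section 13.6 counts grade 3-4 events that have not come down to grade 2 after four weeks off drug, so each candidate event must be observed for four weeks after stopping. Men removed for toxicity supply these events, and they are the men for whom Section 7.5 lets new therapy end follow-up. Section 13.6 does not say how to count an event whose four-week status is unknown.

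**Working it through.** **Step 1. Clauses side by side.**

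| Clause | Governs | Is new therapy a stop? |
|---|---|---|
| 7.5, first sentence | new AEs, all subjects, at least 30 days | no |
| 9.5.1 | new AEs, 30 days, related ones excepted | no |
| 9.1.2 and 9.5.1 | SAEs including death, 30 days | yes, unless judged related |
| 9.1.8 | all deaths within 30 days | no |
| 7.5, second sentence | known event, removed for toxicity | yes |
| 9.1.8 and 9.5.2 | known event | no |

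Each kind of rule contains a disagreement.

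**Step 2. Known event.** Count days from the last dose. Section 7.4 allows removal for toxicity not recovered in 2 weeks, so removal can come at day 14. Suppose new therapy starts on day 18 (an assumed date). Under the second sentence of 7.5, read as a cap, follow-up ends on day 18, which is 28 − 18 = 10 days before the four-week point. Under the first sentence of 7.5 it runs to at least day 30, and under 9.1.8 and 9.5.2 to resolution or stabilization. The four-week grade is observed under the last three clauses and not under the first.

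**Step 3. New event.** Suppose new therapy starts on day 10 and a serious event not judged related occurs on day 20 (assumed dates). Since 20 ≤ 30, it is a collectable adverse event. Since 20 > 10, it is no longer a reportable SAE. If it is a death, 9.1.8 requires a report and 9.1.2 does not. If it is judged related, it is reportable and the conflict disappears.

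**Step 4. Scheduling.** An end-of-treatment visit on day d leaves 30 − d days of the minimum window after it: 29 days if d = 1, 2 days if d = 28. No adverse-event contact is scheduled at day 30.

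**Step 5. The stopping rule.** Inputs from Section 13.6 and Table 9: a beta(2,6) prior, hold if P(risk > 0.30) is at least 65%, and boundaries of 2 events in 2 patients, 3 in 3-6, 4 in 7-9 and 5 in 10-12. The boundaries reproduce from the posterior. Exact enumeration over 12 patients reproduces Table 10 within 1.3 points:

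| True risk | 0.15 | 0.25 | 0.30 | 0.35 | 0.40 | 0.45 | 0.50 |
|---|---|---|---|---|---|---|---|
| Table 10, % stopped | 7.4 | 26.5 | 39.8 | 52.3 | 67.8 | 78.6 | 86.3 |
| Exact, % stopped | 7.6 | 26.9 | 40.0 | 53.6 | 66.5 | 77.5 | 86.1 |

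The rule is therefore sound as specified. To see what one event does, take 6 patients and use P(Beta(a,b) > x) = P(Bin(a+b−1, x) ≤ a−1):

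- 3 events: Beta(5,9), P(Bin(13, 0.3) ≤ 4) = 0.654, so hold.
- 2 events: Beta(4,10), P(Bin(13, 0.3) ≤ 3) = 0.0097 + 0.0540 + 0.1388 + 0.2181 = 0.421, so continue.

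One event left unclassified moves the decision from hold to continue.

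**Step 6. Illustration only.** If a share m of qualifying events went uncounted, the rule would act on risk × (1 − m). At a true risk of 0.40 the chance of a hold would be 66.5% for m = 0, 56.3% for m = 10%, 45.4% for m = 20% and 34.6% for m = 30%. The documents give no basis for any value of m.

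**The case against.** The case against is substantial, and much of it stands.

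- **A reader might infer that adverse-event follow-up ends at the end-of-treatment visit, perhaps the day after the last dose.** No section says so. The visit is an assessment inside a window that runs to at least day 30, and the calendar marks adverse-event notation at long-term follow-up as well. What remains is a scheduling gap, and a mismatch between that calendar column and Section 7.5.1.
- **A reader might infer that follow-up ends flatly at 30 days and late toxicity is missed.** Section 7.5 states a minimum, Section 9.5.1 excepts related events, and related SAEs are reportable without limit. Section 13.3 defines the safety endpoint by drug-related events, the ones these exceptions protect. An unrelated SAE after new therapy is still collected as an adverse event; only the SAE report lapses. The protection is weaker than it looks, though: Section 9.3.3 calls an event related only if no other cause, including other therapies, can be identified, and a new cancer drug often supplies one.
- **The second sentence of 7.5 may extend the 30-day floor and not cap it.** On that reading four weeks are covered. Section 8.1 also allows interruptions of up to 4 weeks before permanent discontinuation, so some men reach four-week status before removal. Both points hold, but the sentence ends follow-up at the earliest of its listed events, which reads naturally as a cap, and Section 7.4 permits removal at two weeks.
- **Two-monthly disease monitoring provides further contact.** It does for some men, but under Section 7.5 it too ends at new antineoplastic therapy.
- **Section 13.6 does not say an unclassified event is left out.** Correct. It gives no rule either way, and that silence is the gap.

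**Conclusion.** The concern holds as a conflict between clauses, with two parts: new therapy ends follow-up of a known event in Section 7.5 but not in 9.1.8 or 9.5.2, and it ends SAE reporting (unless related) but not adverse-event collection or death reporting within 30 days. The missing day-30 contact is a lesser scheduling gap.

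The main consequence is for the stopping rule. It rests on reading the second sentence of 7.5 as a cap and on a man starting new therapy within four weeks of his last dose. Given both, his event may never be classified, and with boundaries of 2 to 5 events a single case can decide a hold.

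A reader might take the falling hold probabilities in Step 6 as the size of the damage. They are not: the documents give neither the time to next therapy nor the rate of late or unresolved events, so the effect cannot be quantified. The text should be corrected because this is cheap and protects the trial's one formal toxicity rule; the finding does not invalidate the design.

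**What to change.** 1. Reconcile Section 7.5 with 9.1.8 and 9.5.2 so that new therapy does not end follow-up of a grade 3-4 event before the four-week point that 13.6 needs.
2. Use one window in 7.5, 9.1.2, 9.1.8 and 9.5.1: adverse events, SAEs and deaths through 30 days after the last dose. Keep the provision for later related SAEs. Record the start date of any new therapy so that events can be shown before and after it.
3. Add an adverse-event check by phone or chart at day 30 when the end-of-treatment visit is earlier, and align Section 7.5.1 with the calendar's long-term column.
4. State in 13.6 that an event above grade 2 at last observation, with unknown four-week status, counts as a safety event.

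The cost is wording and at most one extra contact per patient. There are two downsides. Some events after new therapy will need attribution. Item 4 will count some events that might have resolved by four weeks, so the rule would hold enrollment slightly more often than Table 10 describes for the same true risk. That should be acknowledged beside the table.

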#### 5.0 PATIENT SELECTION

# 5.1 Inclusion Criteria

Patients are eligible to be included in the study only if they meet *all* of the following criteria:

- [1] Have metastatic castration-resistant prostate cancer (prostate cancer progressing by PSA (rise by 25% on prior therapy) or imaging despite castrate levels of testosterone [<50 ng/dL] using standard measures of progression defined by Prostate Cancer Working Group).
- [2] Have a minimum PSA of 1 ng/mL.
- [3] Have a pathological diagnosis of prostate carcinoma.
- [4] Have been receiving and will continue to receive continuous hormonal ablation with surgical or medical castration with baseline testosterone <50ng/dL.
- [5] May be receiving bone-targeted agents.
- [6] May have received multiple lines of therapy including radium 223, sipuleucel T, and up to 2 lines of chemotherapy (One of 2 lines may be for hormone sensitive metastatic prostate cancer or both can be for castration resistant).
- [7] Age  $\geq$  18.
- [8] Have ECOG performance status 0-1 (Appendix A).
- [9] Be able to take oral medication and willing to consider a port for ease of administration of ascorbate.
- [10] Must have progressed on one systemic line of treatment (can include LHRH agonist/antagonist or orchiectomy and at least one additional line of therapy (abiraterone, enzalutamide, apalutamide, darolutamide, docetaxel, etc)).
- [11] Have normal organ and marrow function measured within 28 days prior to administration of study treatment as defined below:

- Absolute neutrophil count  $>1.5 \times 10^9/L$ -Platelets  $> 100,000/mm^3$ 

-Hemoglobin > 9g/dL with no blood transfusion in the

past 28 days

-Total bilirubin < 1.5 x ULN

-AST (SGOT)/ALT(SGPT)  $\leq$  2.5 x ULN (<5x ULN if with known liver

metastases provided bilirubin is normal

-Creatinine  $\leq$  1.6 x ULN (for patients with  $\geq$  1.6 x ULN, calculated

or measured creatinine clearance must be > 60

mL/minute (Cockcroft-Gault).

- [12] Men of reproductive potential and those who are surgically sterilized (i.e. post-vasectomy) must agree to practice effective barrier contraception that has an expected failure rate of <1% during and for 6 months after discontinuation of study treatment. Female partners should also use a highly effective form of contraception ([see **Appendix C** for acceptable methods]) if they are of childbearing potential.

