## 13.8 Analysis of Secondary Endpoints

The **safety analysis** will be performed in all subjects receiving combination olaparib and IV ascorbic acid. AE data will be listed individually and incidence of AEs summarized by system organ class and preferred terms within a system organ class for each treatment group. When calculating the incidence of AEs, each AE (based on preferred terminology defined by Medical Dictionary for Regulatory Activities (MedDRA; Version 13.1, or later) will be counted only once for a given subject. In analyses of grade and causality, if the same AE occurs on multiple occasions, the highest grade and strongest relationship to study drug will be assumed. If 2 or more AEs are reported as a unit, the individual terms will be reported as separate experiences. Changes in vital signs, hematology and clinical chemistry parameters from baseline to the end of the study will be examined. Toxicity will be tabulated by type and grade. Toxicities will be characterized according to the CTCAE version 5.0 Treatment-emergent changes from normal to abnormal values in key laboratory parameters will be identified.

Radiographic progression-free survival (**rPFS**) is defined as the number of months from initiation of therapy (cycle 1, day 1) to date of first radiographic progression, death from any cause, or last patient evaluation. Patients must receive at least one dose of olaparib and IV ascorbic acid to be considered evaluable. Radiographic progression will be determined by modified RECIST criteria 1.1 by development of two or more new bone lesions not consistent with tumor flair for prostate cancer working group 2. Patients who have not progressed or died will be censored at the last date they were assessed and deemed progression-free. rPFS will be summarized and six month estimates for rPFS will be reported using the Kaplan-Meier method with 90% confidence intervals.

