**PSA doubling time** from baseline is a time-to-event outcome. Time in months is measured from the initiation of therapy (cycle 1, day 1) until the PSA has increased to 200% of baseline value after a minimum of 12 weeks of therapy and has been confirmed with another measurement at least 4 weeks later, or death. The date of PSA doubling will be the first value recorded (not the confirmatory value). Patients must receive at least one dose of olaparib and IV ascorbic acid to be considered evaluable. PSA doubling time will be summarized using the Kaplan-Meier method with 90% confidence intervals.

Prostate-specific antigen progression-free survival (**PSA PFS**) is defined as the number of months from initiation of therapy (cycle 1, day 1) to first PSA failure (two consecutive increases in PSA of 50% at least 4 weeks apart and ≥5 ng/mL above nadir) or death. Patients must receive at least one dose of olaparib and IV ascorbic acid to be considered evaluable. Patients who do not experience PSA failure or die will be censored at the last date of PSA measurement. PSA PFS will be summarized using the Kaplan-Meier method with 90% confidence intervals.

**OS** is defined as the number of months from the initiation of therapy to death due to any cause. Patients who are alive or lost to follow up as of the data analysis cutoff date will be

censored at the last date they were assessed. OS will be summarized using the Kaplan Meier method with 90% confidence intervals.

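### Scheduled imaging stops after removal for PSA doubling or symptoms, although neither is an rPFS event, so rPFS can be informatively censored; at low entry PSA, doubling can also fall short of the PSA PFS rule

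*Combined protocol and SAP*

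**What the plan says.** **Leaving treatment.** The removal criteria in Section 7.4 include "Disease progression by symptomatic assessment" and "PSA doubling from baseline value, confirmed by a second value at least 4 weeks apart", the latter only once 12 weeks have passed since therapy began. Section 7.4.1 opens with "Progression will be evaluated on the basis of biochemical, radiographic, or symptomatic progression based on PCWG3 criteria, or by PSA doubling from baseline" and then lists radiographic progression, symptomatic or clinical progression, and PSA doubling as its three definitions.

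**Imaging afterwards.** Section 7.5, repeated in the long-term follow-up footnote of the Study Calendar (Section 7.1), reads "Subjects who discontinued study treatment without documented disease progression should continue to be monitored for disease status by radiologic imaging". This imaging runs every two months and ends at new therapy, disease progression, death, withdrawal or study closure. Neither place restricts progression to the radiographic kind. At end of treatment, Section 7.4.2 asks for scans from a patient who is leaving the study, "if these have not been performed in the prior 3 months". The calendar instead makes that scan depend on clinical indication. Section 7.5.1 collects survival and progression dates every 6 months by phone or chart review and requires no scan.

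**Endpoints.** Under Sections 13.3 and 13.8 an rPFS event is radiographic progression or death from any cause, and "Patients who have not progressed or died will be censored at the last date they were assessed and deemed progression-free". PSA PFS needs two consecutive increases of 50% that are also at least 5 ng/mL above nadir, or death, and "Patients who do not experience PSA failure or die will be censored at the last date of PSA measurement". Eligibility requires only that patients "Have a minimum PSA of 1 ng/mL" (Section 5.1). Time to PSA doubling is a separate secondary endpoint.

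**The concern.** Progression has a wide meaning where the protocol decides who is still scanned and a narrow one where the analysis decides who has an event. A patient removed for PSA doubling or symptoms falls between the two: he has progressed for follow-up purposes, so scheduled scans end, but he has had no rPFS event. If nothing else is recorded, he is censored at his last clean scan.

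Kaplan-Meier estimation assumes that censored patients carry the same future risk as those still observed. Men whose PSA has doubled, or who have worsening symptoms, probably carry more. If so, median rPFS (a stated secondary objective) and the 6-month rPFS estimate in Section 13.8 are too high.

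PSA PFS has a related but separate problem. Removal is relative to baseline, while PSA failure carries an absolute minimum of 5 ng/mL above nadir. At low entry PSA the first can be met before the second. Section 13.8 also has no rule for new therapy in PSA PFS, so a PSA drawn on the next drug could lengthen it.

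**Working it through.** **Plan's own figure.** No design figure exists for rPFS or PSA PFS. The one that does exist is the PSA50 rule in Section 13.5 (12 patients, 2 or more responses, 3% against 23%), and it reproduces: 1 − 0.97¹² − 12(0.03)(0.97¹¹) = 0.0486 and 1 − 0.77¹² − 12(0.23)(0.77¹¹) = 0.801. Nothing below touches it.

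**Does the end-of-treatment scan close the gap?** Scans are every 12 weeks, give or take 1 week. Under Section 13.8 a doubling counts only after 12 weeks and must be confirmed at least 4 weeks later, so take removal at week 16 or 20. With a clean scan at week 12, the last scan is 16 − 12 = 4 or 20 − 12 = 8 weeks old. Both are inside the 3-month waiver, so Section 7.4.2 asks for no new scan, and rPFS can be censored at week 12. A patient removed for symptoms before week 12 may have no scheduled scan after baseline.

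**Size for rPFS.** The documents give none of the inputs, so these are illustrations on assumed values. Both use 12-weekly scans, exponential times linked by a Gaussian copula, no removal before week 16 and no end-of-treatment scan. Each compares the 6-month Kaplan-Meier estimate with imaging continued for everyone against the estimate with removed patients censored at their last scan.

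- *Set 1.* Median time to radiographic progression 20–26 weeks and to removal 20–26 weeks. Between 32% and 54% of patients are removed before radiographic progression is seen. There is no inflation at correlation 0 and about 3–8 points at correlations 0.3–0.7 (for example 53% becomes 61% at 0.7).
- *Set 2.* Median time to radiographic progression 4 months and to removal 4–6 months. Between 27% and 47% are removed first.

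| Set 2 correlation | Imaging for all | Removed patients censored | Inflation (points) |
|---|---|---|---|
| 0 | 38% | 38–39% | 0.0–0.2 |
| 0.5 | 38% | 43–45% | 4.5–6.4 |
| 0.8 | 38% | 45–49% | 6.5–10.9 |

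In Set 2 the median stayed at 5.52 months under this censoring, because events can only be seen on the 12-week scan grid. The 6-month estimate is the more sensitive summary.

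**PSA PFS thresholds.** Let B be entry PSA. Removal is at 2B. Reading both values against nadir, failure needs max(1.5 × nadir, nadir + 5). With nadir = B the two levels cross where 2B = B + 5, so B = 5. At exactly 2B, failure requires nadir ≤ 2B − 5.

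| B (ng/mL) | Removal, 2B | Failure level if nadir = B | Nadir needed at exactly 2B |
|---|---|---|---|
| 1 | 2 | 6 (6.0 × B) | impossible |
| 2 | 4 | 7 (3.5 × B) | impossible |
| 3 | 6 | 8 (2.67 × B) | ≤ 1 (67% fall) |
| 4 | 8 | 9 (2.25 × B) | ≤ 3 (25% fall) |
| 5 | 10 | 10 (2.0 × B) | ≤ 5 (no fall) |

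Below B = 2.5 a value of exactly 2B can never qualify, since 2B − 5 is negative.

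Example: B = 2 with a 13-week doubling time from the start gives 2 × 2^(16/13) = 4.7 at week 16 and 2 × 2^(20/13) = 5.8 at week 20. Doubling is confirmed, but the failure level of 7 is not reached until 13 × log₂(3.5) = 23.5 weeks.

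**The case against.** **Not every such patient is censored.** A reader might infer that all men removed on these grounds are counted as progression-free. The documents do not support that. Death is an event in both endpoints, and long-term follow-up collects radiographic and PSA progression dates. This stands, but it does not close the gap. No scan is required, and no rule says how a chart-derived date is used after new therapy or how a death after a gap in scans is handled. Late deaths do not repair the estimate either. In Set 2, with an assumed median of 10 months from radiographic progression to death, counting later deaths at the death date gives 47–52% at 6 months against 38% with imaging for all, and this excess appears even at correlation 0.

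**The wording is ambiguous.** Section 7.4 lists PSA doubling apart from the items it calls disease progression, and a doubling could itself prompt a clinically indicated scan. That is a possible reading, but Section 7.4.1, under the heading Disease Progression, includes doubling and symptoms outright. The two end-of-treatment scan rules differ and need reconciling in any case.

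**Entry PSA below 5 does not by itself mean censoring in PSA PFS.** Correct. For the doubling mismatch, on the reading of both values against nadir, it is necessary but not sufficient: a prior fall or a rise well beyond 2B can meet the rule. PSA is also drawn at end of treatment, up to 28 days after the last dose, and the calendar marks it in long-term follow-up. In the example PSA is 7.2 at week 24, though a second qualifying value would still be needed. For removal on symptoms the 5 ng/mL minimum is not what matters: such a man is censored at any entry PSA if he has not met PSA failure.

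**The stakes are modest.** These endpoints are descriptive. With 12 patients the 90% half-width at 53% is about 1.645 × √(0.53 × 0.47/12) = 24 points, well above the bias illustrated. True, but imprecision is visible in the interval and bias is not.

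**Continued imaging would still stop at new therapy.** Also true. Section 7.4.1 links leaving treatment to the need for new therapy, so many patients would leave imaging soon anyway.

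**Conclusion.** The point holds as a mismatch of definitions. Read together, Sections 7.4, 7.4.1 and 7.5 end scheduled imaging after PSA doubling or symptomatic progression, while rPFS recognises neither. Affected patients can be censored at their last clean scan, and the rPFS estimate is too favourable if these forms of progression are positively correlated with radiographic progression.

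The size cannot be derived from the documents. Under the assumed inputs above, the censoring adds 0 points to 6-month rPFS at correlation 0 and roughly 3 to 11 points at correlations of 0.3 to 0.8. With 27–54% of patients removed first, about 3 to 6 of 12 men would be involved.

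For PSA PFS, a man with entry PSA from 1 to below 5 ng/mL can be removed for confirmed doubling without having met PSA failure, depending on his nadir and on how far PSA exceeds twice baseline. The share of patients in that range is not given. He is not lost from the PSA results, because he is an event for time to PSA doubling. A reader should not infer any effect on the primary PSA50 endpoint or its decision rule; there is none.

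**What to change.** 1. In Section 7.5 and the Study Calendar's long-term follow-up footnote, make the condition for continued imaging the absence of documented *radiographic* progression, and make the second stopping condition radiographic progression. Keep the two-monthly schedule and the stop at new therapy. This reduces the bias but does not remove it. The cost is a few additional scans.
2. In Section 13.8, add an rPFS sensitivity analysis that counts removal for PSA doubling or symptomatic progression as an event, and report the number of patients censored by reason.
3. Leave the PSA PFS event definition as it is. Folding doubling into it would merge two endpoints that the plan keeps separate. Report instead how many patients removed for PSA doubling were censored in PSA PFS, and add a sensitivity analysis that censors PSA PFS at the start of new anticancer therapy.

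Items 2 and 3 use data already collected and cost a few lines of text and a small amount of analysis. They can stand alone if the extra scans in item 1 are not wanted.
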